5.3.2.1.2. Other Reasons, and Procedures, for Permanent Discontinuation of Investigational Product

As much as possible and permitted by the protocol, subjects should be encouraged to continue on IP for the full 24-month Treatment Period.

Subjects have the right to permanently discontinue IP at any time for any reason. Investigators may also discontinue IP if they determine that it is not in the best interest of the subject to continue. All subjects should be encouraged to remain in the study even if IP has been discontinued for any reason.

IP must be permanently discontinued if the subject meets any of the following criteria:

- Subject permanently discontinues XOI.
- Subject becomes pregnant.
- Subject initiates chronic therapy with any of the following medications:
 - valpromide, progabide, valproic acid, or other known inhibitors of epoxide hydrolase.
 - any approved ULT indicated for the treatment of gout (eg, benzbromarone, probenecid, pegloticase, commercially-available lesinurad), except those required per protocol (allopurinol and febuxostat).
 - azathioprine or mercaptopurine.
- Subject requires dialysis or kidney transplantation.
- Subject has temporarily interrupted IP for more than 3 separate episodes at any time on study due to changes in kidney function, based on any safety concern due to IP by the Investigator or Healthcare Provider, or where protocol-specified criteria for interruption have been met (ie, sCr \geq 4.0 mg/dL or an eCrCl $<$ 20 mL/min).

The date and the reason must be recorded on the appropriate Case Report Form (CRF) for all subjects who discontinue IP. If the reason is an AE, the specific AE must be identified on the CRF.

Subjects who permanently discontinue IP early should complete an End of Treatment Visit (Section 8.3.3) as soon as possible followed by a Post-End of Treatment Visit (Section 8.4.1) 1 month after the End of Treatment Visit. Subjects should then continue on study and follow the protocol-defined schedule of events, through Month 24. The subject has the option to continue on study-supplied XOI during this time. Although all assessments are encouraged, at a minimum, it is requested that collection of AEs and collection of a blood sample for Analytes 1 (see Table 1) occur. Alternatively, if the subject does not agree to this option, a modified follow-up including, eg, regular telephone contacts or a contact at Month 24, should be arranged, if agreed to by the subject and in compliance with local data privacy laws/practices. Subjects who do not wish to continue on study after discontinuing IP should complete an End of Study Visit (Section 8.4.2) 1 month after treatment discontinuation.

If IP is permanently discontinued prior to the Month 6 study visit, then gout flare prophylaxis should also be discontinued.

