6.14. Suspected Pregnancy (Exposure in Utero)

If a subject becomes pregnant, IP, XOI, and gout flare prophylaxis (if applicable) should be discontinued immediately. The Investigator or other site personnel must notify the Sponsor or designee of a pregnancy associated with IP exposure within 1 day; ie, immediately, but **no later than 24 hours**, after the Investigator becomes aware of it and record the event and the course of the pregnancy, including perinatal and neonatal outcome (when is known) on the Pregnancy Report Form that will be provided to each site. The same timelines apply when outcome information is available.

Pregnancy itself is not regarded as an AE unless there is a suspicion that the IP under study may have interfered with the effectiveness of a contraceptive medication. Congenital abnormalities/birth defects and spontaneous miscarriages should be reported and handled as SAEs. Elective abortions without complications should not be handled as AEs. The outcome of all pregnancies (spontaneous miscarriage, elective termination, ectopic pregnancy, normal birth, or congenital abnormality) should be followed up and documented even if the subject was withdrawn from the study. Partner pregnancy data may not be collected.

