7.1.2.1. Allopurinol

Drugs that should not be administered or should be administered with caution while taking allopurinol include, but are not limited to, the following:

- 6-mercaptopurine
- azathioprine
- coumarin anticoagulants
- theophylline
- captopril
- ampicillin/amoxicillin
- cyclosporine
- didanosine
- vidarabine (adenine arabinoside)
- oxipurinol
- thiazide diuretics
- cyclophosphamide
- tolbutamide
- chlorpropamide

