7.1.2.2. Interactions With Febuxostat

Febuxostat should not be administered with 6-mercaptopurine or azathioprine.

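### After pregnancy or a chronic start of azathioprine or mercaptopurine, protocol Section 5.3.2.1.2 stops IP but leaves study-supplied XOI optional, in conflict with Section 6.14 and, for febuxostat, Section 7.1.2.2

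*Combined protocol and SAP*

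**What the plan says.** Protocol Section 5.3.2.1.2 opens its list of mandatory triggers with "IP must be permanently discontinued if the subject meets any of the following criteria". Two of the triggers matter here. One is "Subject becomes pregnant". The other is "Subject initiates chronic therapy with any of the following medications", under which the protocol names "azathioprine or mercaptopurine".

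The same section then describes what follows for subjects who stop IP early. They stay on study through Month 24, and "The subject has the option to continue on study-supplied XOI during this time". Section 3.1 repeats this permission. Section 8.3.3 lists XOI dispensing at the Month 24/End of Treatment Visit with no qualifier. Section 8.4 has subjects who stopped IP follow the normal schedule and excepts only the dispensing and taking of IP.

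Three other sections address XOI in the same circumstances:

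- Section 6.14: "If a subject becomes pregnant, IP, XOI, and gout flare prophylaxis (if applicable) should be discontinued immediately".
- Section 7.1.2.2: "Febuxostat should not be administered with 6-mercaptopurine or azathioprine".
- Section 7.1.2.1: "Drugs that should not be administered or should be administered with caution while taking allopurinol include, but are not limited to, the following". The list that follows includes 6-mercaptopurine and azathioprine.

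Section 7.1.1, on interactions with lesinurad, names neither drug.

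**The concern.** A site that learns of a pregnancy, or of a new prescription for azathioprine or mercaptopurine, will probably turn first to the section that governs stopping IP. That section names the event, tells the site to stop IP, and says the subject may stay on study-supplied XOI. Nothing there signals that another section limits or removes that choice.

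The only interactions the protocol describes for azathioprine and mercaptopurine are with the XOIs, which are the drugs Section 5.3.2.1.2 leaves available. Section 7.1.2 introduces these interactions as potentially serious. The study also supplies the XOI, so the inconsistency reaches dispensing as well as advice. What is at stake is the safety of the individual subject, not the statistical analysis.

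**Working it through.** No arithmetic applies: the point depends on no sample size, rate, margin or power. The check sets the current texts side by side, trigger by trigger.

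| Trigger and XOI | Section 5.3.2.1.2 on XOI | Other section on XOI | Result |
|---|---|---|---|
| Pregnancy, either XOI | Optional continuation | 6.14: stop at once, with IP and prophylaxis | Direct conflict |
| Azathioprine or mercaptopurine, febuxostat | Optional continuation | 7.1.2.2: not to be given together | Direct conflict |
| Azathioprine or mercaptopurine, allopurinol | Optional continuation | 7.1.2.1: avoid or use with caution, not said which | Omitted restriction |

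1. **Is the option conditional on why IP was stopped?** No. It applies to subjects who permanently discontinue IP early, as a group. Section 3.1 is equally general.

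2. **Does Section 5.3.2.1.2 limit the option by cross-reference?** No. It points to the visit sections (8.3.3, 8.4.1, 8.4.2) and to Table 1, but not to 6.14 or 7.1.2.

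3. **Does the trigger list deal with XOI at all?** In one direction only: permanently stopping XOI is a trigger for stopping IP. Nothing in the list makes pregnancy or these two drugs a trigger for stopping XOI.

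4. **Do the visit schedules settle the matter?** Not in either direction. Section 8.3.3 lists XOI dispensing without a qualifier, but that list also serves subjects completing Month 24. Section 8.4.1 makes dispensing at the Post-End of Treatment Visit conditional on its being applicable. Appendix A shows XOI-only dispensing at both visits, and its footnote j says dispensing and compliance checks are not required once IP has been permanently stopped. Read together, the schedules permit XOI dispensing to these subjects and do not require it.

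5. **If the option is used with allopurinol, does the follow-up carry over any caution?** Section 7.1.2 explains that caution may mean dose adjustment or extra monitoring. The minimum follow-up requested in Section 5.3.2.1.2 is adverse events and the Analytes 1 panel (blood urea nitrogen, creatinine, glucose and uric acid). It mentions no adjustment or monitoring for an interaction.

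6. **Does the protocol handle a comparable case explicitly?** Yes. Section 5.3.2.2.1 says what must happen to colchicine when an interacting drug is needed and refers to Section 7.1.3. There is no equivalent sentence for XOI.

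**The case against.** The strongest reply is that Section 5.3.2.1.2 gives a permission and no instruction to administer XOI. On this view the specific sections limit a general option, and an experienced site would read them together. A site handling a pregnancy needs Section 6.14 anyway, for the 24-hour notification and the report form. Section 7.1.2 tells investigators to be aware of XOI interactions and to consult local labels, the labeling is supplied to them (Section 5.2), and Section 5.3.2.1 allows XOI to be interrupted for adverse events or suspected toxicity.

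This lowers the chance that a site goes wrong, but it does not remove the inconsistency. Section 5.3.2.1.2 names these very triggers and sets out what follows, without an exception or a pointer. Reading 6.14 as the specific rule helps only with pregnancy. Label references do not reconcile two statements in the protocol itself.

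The objection does rule out several stronger readings that a reader might infer:

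- **That the option contradicts all of Section 7.1.2.** It does not. For allopurinol, optional continuation is compatible with the caution reading of Section 7.1.2.1.
- **That Appendix A obliges sites to dispense XOI.** Footnote j and the conditional wording in Section 8.4.1 say otherwise.
- **That only IP is stopped.** Section 5.3.2.1.2 also stops gout flare prophylaxis if IP ends before the Month 6 visit. XOI is the component left open.
- **That the adverse event comparison is compromised.** Section 9.4.2.2 plans both on-treatment and on-study analyses, so counting events after IP stops is intended. The option applies to both blinded arms, and nothing in the documents points to a differential effect.

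**Conclusion.** The concern holds in a limited form. There are two direct conflicts: pregnancy (Section 5.3.2.1.2 against 6.14), and azathioprine or mercaptopurine with febuxostat (Section 5.3.2.1.2 against 7.1.2.2). With allopurinol, Section 5.3.2.1.2 leaves out a restriction that Section 7.1.2.1 signals without defining.

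Few subjects should be affected. Section 4.3 excludes users of azathioprine or mercaptopurine and pregnant subjects, so only on-study starts and on-study pregnancies count. The documents give no rate for either, and any number of subjects would be a guess. No endpoint, estimand or planned analysis changes.

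The importance lies in conflicting guidance on a study-supplied drug in situations the protocol itself treats as safety matters. The conclusion rests on the current wording alone. It takes no position on whether XOI should stop or continue in any of these cases.

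**What to change.** Reconcile Sections 3.1, 5.3.2.1.2, 8.3.3, 8.4, 8.4.1 and Appendix A (with footnote j) with Sections 6.14 and 7.1.2 to 7.1.2.2, as follows:

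- For each trigger in Section 5.3.2.1.2, state whether it applies to IP, to XOI or to both.
- Where the option to continue study-supplied XOI is given, state any exceptions, or state why it may continue, and cross-refer to Sections 6.14 and 7.1.2.
- In Section 7.1.2.1, say which of the two categories, avoidance or caution, applies to azathioprine and mercaptopurine.
- Align the XOI dispensing entries in Section 8.3.3 and Appendix A with the result.

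The sponsor's clinical team must decide which instruction stands in each case. The cost is amendment wording and a site memo; no new data, visits or subjects are needed.

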5.3.2.2. Gout Flare Prophylaxis

Gout flare prophylaxis should generally only be continued through the Month 6 study visit as tolerated (ie, colchicine alone, or if colchicine is replaced with oral corticosteroids). It is recognized that if oral corticosteroids alone are used for gout flare prophylaxis, the course will generally be shorter. If XOI and IP are interrupted, gout flare prophylaxis may be re-initiated when the study medications are resumed per the discretion of the Investigator based on the clinical circumstances. If IP is permanently discontinued prior to the end of the gout flare prophylaxis period, the gout flare prophylaxis should be discontinued.

5.3.2.2.1. Colchicine

Subjects are required to continue gout flare prophylaxis with colchicine through their Month 6 study visit unless they become intolerant or develop toxicity to the colchicine. Gout flare prophylaxis with colchicine may be interrupted or discontinued prior to the expected Month 6 study visit due to an AE or tolerability. If colchicine is interrupted for any reason in the gout flare prophylaxis period, it should be restarted when medically appropriate. Subjects should be encouraged to continue on colchicine as tolerated through the Month 6 study visit, but may decrease the dose or increase the interval between doses (ie, from once daily to once every other day).

If a subject requires treatment with cyclosporine, ranolazine, or strong/moderate CYP3A inhibitors (eg, clarithromycin, fluconazole, diltiazem; see [Section 7.1.3](#)) prior to their Month 6 study visit, then colchicine must be interrupted or discontinued.

Subjects who are unable to take colchicine during the gout flare prophylaxis period should, when medically appropriate, switch to a short course of low-dose oral corticosteroids. If switching is not medically appropriate, randomized subjects may continue in the study without gout flare prophylaxis.

5.3.2.2.2. Low-Dose Corticosteroids

Subjects unable to take colchicine (ie, those who have a documented intolerance or allergy to colchicine or who initiate a concomitant medication contraindicated for use with colchicine [eg, P-gp or strong CYP3A4 inhibitors]) are permitted to take low-dose oral corticosteroids (ie, ≤ 10 mg/day of prednisone, or prednisolone, or their equivalent) for a short course, such as through the Month 3 study visit, at the discretion of the Investigator, individualizing for each subject the need for gout flare prophylaxis and potential side effects of persistent steroid use, such as in relation to comorbid conditions.

Gout flare prophylaxis with corticosteroids may be interrupted or discontinued due to an AE or tolerability. Subjects should be encouraged to continue on low-dose corticosteroids through the Month 3 study visit but may decrease the dose as needed.

5.4. Method of Assigning Subjects to Treatment Groups

Approximately 600 subjects will be randomized in a 1:1 ratio to lesinurad 200 mg or placebo in combination with an XOI. Subjects will be randomized at their Baseline Visit after the Investigator has verified that they meet all of the study eligibility criteria ([Section 4.2](#) and [Section 4.3](#)) and after all screening assessments have been completed ([Appendix A](#)).

Randomization will take place across all study sites using a centralized Interactive Voice Response System/Interactive Web Response System (IVRS/IWRS) and will be stratified by Screening eCrCl (30.0 to <45.0 mL/min or 45.0 to <60.0 mL/min), Baseline measurable target tophus status (present/absent), and type of XOI (allopurinol or febuxostat).

Subject randomization numbers will be generated by the IVRS/IWRS company. Subject eligibility information will be provided by the Investigator or the Investigator's research staff to the IVRS/IWRS at randomization. Two site staff members must verify the information entered into the IVRS/IWRS prior to randomization to ensure accuracy and reduce stratification errors. Each subject meeting eligibility criteria and completing all Screening assessments will be randomized, assigned a unique randomization number, and a randomization confirmation will be sent by the IVRS/IWRS to the site.

No subject may begin IP prior to randomization and assignment of a randomization number. Subjects who have been randomized but withdraw from the study may not be replaced.

5.5. Blinding

Treatment group assignments will be blinded to minimize bias in study assessments and monitoring. In order to maintain the blind, the randomization list generated by the IVRS/IWRS, as well as sUA results post-Baseline, will not be available to subjects, study site staff, or the Sponsor's project team (including the team at the Clinical Research Organization, as applicable) until after database lock with the following exceptions:

- The Clinical Trials Material [CTM] staff is authorized to receive the randomization list to facilitate drug packaging and monitor site inventory for IP.
- The Good Manufacturing Practice Quality Assurance staff is authorized to receive the randomization list to facilitate packaging and release of all CTM.

The IDMC will receive unblinded data to periodically review safety data during the study. For more information on this committee, see [Section 11.8](#).

The pharmacovigilance staff will break the blind only for individual subjects who have SAEs that are both unexpected and suspected to be causally related to IP in order to allow appropriate safety reporting to regulatory authorities. Blinding will not be broken for the planned analyses of data until all decisions on the evaluability of the data from each individual subject have been made and documented.

In the cases of emergency unblinding for safety concerns such as medical emergencies when the appropriate management of the subject requires knowledge of the treatment randomization, the Investigator or designee should contact the Sponsor or designee prior to unblinding a subject's treatment assignment. The IVRS/IWRS will provide the site with the subject's treatment assignment.

5.6. Dispensing Investigational Product

IP will be dispensed at the Baseline Visit and every 3 months thereafter through Month 21 of the Treatment Period. Each bottle will be identified with a unique medication number to protect the blind.

5.7. Packaging and Labeling

IP will be packaged and labeled under the responsibility of the Sponsor in a manner consistent with the study design and according to local regulatory requirements. No repackaging and/or relabeling activities at the study site are allowed. Investigational product will be identified as an investigational compound.

Study site staff should refer to the local product labels for packaging and labeling information for XOIs and gout flare prophylaxis, provided by the Sponsor.

5.8. Study-Supplied Medications Receipt, Storage, Accountability, and Returns

The Investigator must maintain accurate records of all IP, XOI, and colchicine administered as per protocol, including date received, number of units received, and lot number. The Investigator must also ensure that all study-supplied medications are kept secured and accounted for with access limited to only those individuals authorized by the Investigator. The Investigator, his/her designee, or the pharmacist must also maintain adequate records of distribution and dispensing of all study-supplied medications, as well as return of IP to the Drug Depot and destruction of all other study-supplied medications, to be able to reconcile their records (ie, accountability or dispensing logs) periodically throughout the study.

All records must be readily available for inspection by the site monitor and/or auditor. No medications may be returned to the Sponsor or designee (IP) or disposed of at the study site (XOI and colchicine) until the site monitor has verified the accuracy of the records at the study site. All returns, disposals, or destruction must be approved by the Sponsor.

For more complete information regarding study-supplied medication receipt, storage, accountability, return (IP), and destruction (XOI and colchicine), refer to the Study Reference Manual.

5.8.1. Site Receipt of Investigational Product

Within approximately 48 hours upon receipt of study-supplied IP at the study site, the appropriate trained site staff should review the contents and record receipt of the shipment in IVRS/IWRS.

5.8.2. Site Storage

Bottles containing IP must be stored at 15 to 30°C/59 to 86°F. XOI and colchicine should be stored according to the product label. Appropriate storage conditions in the pharmacy or drug storage area must be ensured and temperature must be recorded.

Access to study-supplied medications should be restricted to designated study personnel.

The site monitor should review the supplies of study-supplied medications held by the Investigator or pharmacist at each monitoring visit to ensure accountability and appropriate storage conditions.

5.8.3. Home Storage

The study staff is responsible for providing subjects with instructions on storing all study-supplied medications.

Subjects should be instructed to keep all study-supplied medications in a secure location.

5.8.4. Compliance and Accountability

Accountability will be assessed by maintaining adequate medication dispensing records. Study-supplied medications must be dispensed by a qualified member of the study site staff. Study site staff is responsible for providing subjects with instructions on correct medication administration.

At each study visit, subjects will return all bottles of IP, XO1, and colchicine (used and unused), and study staff will ask about their treatment compliance. The number of tablets returned should be counted and documented in the source documentation. Study site staff is also responsible for accurately completing the subject's medications CRF and appropriate systems (ie, clinical database and IVRS/IWRS).

Study-supplied XO1 and colchicine that are returned may be redispensed to the same subject provided accurate accountability records are maintained.

Subjects will be asked to bring study-supplied IP dispensed at Baseline to their Month 1 study visit for compliance check. This IP will be redispensed to the same subject at the Month 1 visit.

Study-supplied medications that are returned should not be redispensed to a different subject.

5.8.5. Return of Investigational Product to the Drug Depot

After accountability has been verified by the site monitor, IP bottles will be returned to the drug depot. The return will be documented within the source documentation and processed by site monitor in IVRS/IWRS prior to shipment to the depot.

5.8.6. Destruction of XO1/Colchicine

After accountability has been verified by the site monitor, returned supplies of XO1 and colchicine will be destroyed per the study site's process. The destruction will be documented within the source documentation and processed by the site monitor.

